7.0 DOSE DELAY / MODIFICATION GUIDELINES

7.1 Dose Delays/ Modification

- Toxicities will be graded using the NCI CTCAE v 5.0.
- Baseline values are from the last values obtained prior to treatment.
- Both acalabrutinib and umbralisib may be dose reduced for toxicity. If a toxicity occurs, both drugs (as well as ublituximab) may be interrupted until resolution to Grade 1, to baseline, or as noted in Table 7.1.1. Following that, either or both oral agents may be dose reduced based on suspected attribution. General guidelines for recommended dose delays and modifications are provided below.
- No reduction in the dose of ublituximab is permitted. If Grade 4 anaphylaxis is observed at any point during ublituximab treatment, permanently discontinue ublituximab treatment and intervene as per investigator discretion.
- All study drugs may be delayed for a maximum of 8 weeks to allow recovery of toxicities as specified in the tables below.
- If one of the study drugs is discontinued for toxicity, patient may continue therapy with the other study drugs.
- When treatment interruption is required for toxicity, all drugs are held. If ublituximab is suspected to be the primary reason for a recurrent toxic event, it may be discontinued only in consultation with the Study PI.

Table 7.1.1 Recommended Dose Modifications

NCI-CTCAE Grade	Dose Delay and/or Modification
Hematologic Adverse Event	
Neutropenia	
Grade \leq 2 neutropenia	Provide supportive care as warranted. Maintain current dose and schedule of acalabrutinib. Maintain current dose of umbralisib. If applicable, maintain full dose and schedule of ublituximab.
Grade 3 neutropenia	Provide supportive care as warranted. Maintain current dose and schedule of acalabrutinib. Maintain current dose of umbralisib. For recurrent or persistent Grade 3 neutropenia unresponsive to maximum supportive care:

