	
 • If toxicity is suspected to be related to umbralisib by the investigator (e. g. based on timing of toxicity occurrence during the cycle), reduce umbralisib to next lower dose level. If the lowest dose level of umbralisib is reached, reduce acalabrutinib to the next lower dose level. • If toxicity is suspected to be related to acalabrutinib by the investigator (e. g. based on timing of toxicity occurrence during the cycle), reduce acalabrutinib to the next lower dose level. For recurrences, umbralisib may be dose reduced. 
If applicable, maintain full dose and schedule of ublituximab.

Grade 4 neutropenia or occurrence of neutropenic fever or infection	
Provide supportive care as warranted.
 
 • If toxicity is suspected to be related to umbralisib by the investigator (e. g. based on timing of toxicity occurrence during the cycle): 
1st occurrence:
 
 - Delay umbralisib until Grade \leq 1 or baseline and, if present, neutropenic fever or infection is resolved; thereafter, resume umbralisib at current dose. - If grade 4 neutropenia lasts longer than 7 days (despite holding umbralisib), interrupt acalabrutinib until Grade \leq 1 or baseline and, if present, neutropenic fever or infection is resolved; thereafter, resume acalabrutinib at current dose level. 
2nd occurrence (despite maximum supportive care):
 
 - Same as for 1st occurrence, but resume umbralisib at next lower dose level (dose reduction). 
3rd occurrence (despite maximum supportive care):
 
 - Delay umbralisib and acalabrutinib until Grade \leq 1 or baseline and, if present, neutropenic fever or infection is resolved; thereafter, resume umbralisib and acalabrutinib at next lower dose level. 
4th occurrence (despite maximum supportive care):
 
 - Discontinue umbralisib. - If grade 4 neutropenia lasts longer than 7 days (despite umbralisib discontinuation), discontinue acalabrutinib. 
If applicable, delay ublituximab until Grade \leq 3 and, if present, neutropenic fever or infection is resolved; thereafter, resume ublituximab at full dose and schedule.

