Grade 1 or 2	
Provide supportive care as warranted.
 
Maintain current dose and schedule of acalabrutinib.
 
Delay umbralisib. Upon complete resolution, restart umbralisib at next lower dose level.
 
If recurrence after re-challenge, discontinue umbralisib.
 
Hold ublituximab. Upon resolution, resume ublituximab at full dose and schedule. If recurrence after re-challenge, discontinue ublituximab.

Grade ≥ 3	
Provide supportive care as warranted.
 
Discontinue umbralisib.
 
Hold acalabrutinib and ublituximab until complete resolution. Restart at acalabrutinib current dose level and ublituximab at full dose and schedule.
 
If 2nd occurrence, discontinue all drugs

*** For sinopulmonary infections clearly not related to immune-mediated pneumonitis, umbralisib may be continued at investigator's discretion. While pneumonitis has been minimal with umbralisib, it is a reported adverse event associated with other PI3K delta inhibitors. Use of anti-pneumocystis and anti-herpetic viral prophylaxis is required prior to the start of therapy.**

Diarrhea and/or Colitis	
Diarrhea Grade ≤ 2	
Provide supportive care as warranted.
 
Maintain current dose and schedule of acalabrutinib.
 
If tolerable, maintain current dose of umbralisib. Otherwise, delay umbralisib until \leq grade 1. Resume umbralisib at current dose level.
 
NOTE: If persistent grade 2 diarrhea despite supportive care, delay umbralisib until \leq grade 1; thereafter, resume umbralisib at next lower dose level.

	
If recurrence after rechallenge, delay umbralisib until \leq grade 1; thereafter, resume umbralisib at current dose.
 
If applicable, maintain full dose and schedule of ublituximab. If intolerable or persistent grade 2 diarrhea despite supportive care, delay ublituximab until \leq grade 1; thereafter, resume ublituximab at full dose and schedule.

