
Grade ≥ 3 Discuss with the study PI.
	
Monitor labs at least weekly until toxicity fully resolved (Grade 0). Once resolved:
 
 ○ Restart acalabrutinib at current dose level. ○ Restart umbralisib at 400 mg po daily. ○ Restart ublituximab*** at full dose and schedule. ○ Taper prednisone by 10 mg per week until off. 
If 2nd occurrence of liver toxicity Grade ≥ 3:
 
Discontinue umbralisib. Hold acalabrutinib and ublituximab until resolved (Grade 0). Thereafter, resume acalabrutinib at current dose level and restart ublituximab*** at full dose and schedule; however, if liver toxicity is strongly suspected to be related to acalabrutinib, treat as 3rd occurrence below.
 
If 3rd occurrence of liver toxicity to Grade ≥ 3, discontinue acalabrutinib and resume umbralisib at 400 mg po daily and ublituximab*** at full dose and schedule once toxicity resolves (to Grade 0). If toxicity does not recur, umbralisib may be escalated by one dose level after a full cycle of therapy. Re-introduction of acalabrutinib may be attempted after 3 full cycles of therapy in absence of additional liver toxicity, after discussion with the study PI. In those circumstances, acalabrutinib should be given on days 8-28 of each cycle and liver function tests (AST, ALT, bilirubin) checked within 14±7 days after the first dose of acalabrutinib, and as needed thereafter. If liver toxicity recurs to grade ≥ 3, acalabrutinib should be permanently discontinued.
 
If 4th occurrence of liver toxicity Grade ≥ 3 (while on umbralisib), permanently discontinue umbralisib. Re-introduction of acalabrutinib may be attempted after 3 full cycles of therapy in absence of additional liver toxicity, after discussion with the study PI. In those circumstances, liver function tests (AST, ALT, bilirubin) should be checked within 14±7 days after the first dose of acalabrutinib, and as needed thereafter. If liver toxicity recurs to grade ≥ 3, acalabrutinib should be permanently discontinued.

---	---

* Assess for disorders of lipids and glucose, thyroid disorders, alcohol use, viral infections, etc.

**Supportive Care – Aggressive management of lipid, glucose, other metabolic disorders, viral infections, etc.

Important: Before initiating steroids, check for viral hepatitis or CMV infection.

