
 • A maximum of two dose level reductions are allowed for umbralisib. • If a subject requires a dose reduction of umbralisib (or acalabrutinib) due to study drug related toxicity, the dose may not be re-escalated. If further evaluation of the toxicity reveals the event was not related to umbralisib (or acalabrutinib), this should be recorded in the medical record and dose re-escalation to the previous dose may be considered in consultation with the Study PI. • If a subject: 1/ is already at the lowest dose level of umbralisib (or acalabrutinib) following prior dose reduction(s) due to study drug related toxicity, and 2/ experiences a different toxicity that would require a dose reduction, then, in consultation with Study PI, umbralisib (or acalabrutinib) may be delayed and then resumed at the same dose level when the toxicity resolves as indicated in the table for that particular toxicity. • In case of concurrent toxicities, follow the more stringent dose modification recommendations. 			

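### Section 7.1 requires every drug to be held at a toxicity interruption, but several Table 7.1.1 rows delay umbralisib while acalabrutinib continues, and no text says which governs

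*Combined protocol and SAP*

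**What the plan says.** Section 7.1 opens with general bullets, then gives Table 7.1.1 by toxicity and grade, then the dose-reduction table with its notes.

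Two bullets deal with interruption. An early one is permissive and points to the table: after a toxicity, "both drugs (as well as ublituximab) may be interrupted until resolution to Grade 1, to baseline, or as noted in Table 7.1.1". The last one is mandatory and carries no qualifier: "When treatment interruption is required for toxicity, all drugs are held".

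Some rows then separate the two oral drugs. For Grade 1-2 pneumonitis the row says "Maintain current dose and schedule of acalabrutinib" and, for the other oral agent, "Delay umbralisib. Upon complete resolution, restart umbralisib at next lower dose level". For Grade 4 neutropenia attributed to umbralisib, umbralisib is delayed first, and acalabrutinib follows only under a further condition: "If grade 4 neutropenia lasts longer than 7 days (despite holding umbralisib), interrupt acalabrutinib".

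On re-escalation, the notes under the dose-reduction table say that after a reduction for study-drug-related toxicity "the dose may not be re-escalated". The exception is an event found on further evaluation not to be related to the drug, with Study PI consultation. In the liver row for Grade 3 or higher, 3rd occurrence, "umbralisib may be escalated by one dose level after a full cycle of therapy", provided the toxicity has not come back.

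**The concern.** The last bullet and the rows are both instructions for the same moment: a toxicity has occurred and at least one drug must stop. Under the bullet, acalabrutinib stops as well. Under the rows listed below, it continues. A site cannot do both, and either choice can be defended from the text.

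The first stake is patient safety and consistent care across the four participating sites. The second is interpretability. Induction handling precedes the end-of-induction CR assessment, and the final decision turns on whether at least 10 of 24 evaluable patients reach CR (Section 12.1). Febrile neutropenia and Grade 2 or higher pneumonitis are also on the toxicity monitoring list in Section 12.4.2. Section 15.0 adds a practical difficulty: deviations must be reported, yet it is unclear whether following the row or following the bullet would be the deviation.

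**Working it through.** No arithmetic is needed to establish the conflict. The check sets the mandatory bullet against the rows of Table 7.1.1.

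| Row in Table 7.1.1 | Umbralisib | Acalabrutinib | Ublituximab | Compatible with holding every drug? |
|---|---|---|---|---|
| Grade 4 neutropenia attributed to umbralisib, 1st and 2nd occurrence | Delayed | Continues unless Grade 4 exceeds 7 days | Delayed | No |
| Pneumonitis, Grade 1-2 | Delayed | Maintained | Held | No |
| Diarrhea, Grade 2 or lower, if intolerable or if Grade 2 persists | Delayed | Maintained | Delayed | No |
| Grade 4 neutropenia attributed to acalabrutinib | No hold stated | Delayed | Delayed | Row silent on umbralisib |
| Grade 3 thrombocytopenia with bleeding, or Grade 4, attributed to acalabrutinib | No hold stated | Delayed | Delayed | Row silent on umbralisib |
| Liver toxicity, Grade 2 | Delayed | Delayed | Delayed | Yes |
| Other non-hematological event, Grade 3 or higher | Delayed | Delayed | Delayed | Yes |

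The last two rows show that the table stops all three drugs for some toxicities and not for others. The bullet draws no such distinction.

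**Could a delay be something other than an interruption?** The protocol does not define the terms separately. The neutropenia row itself describes the delayed drug as being held: "If grade 4 neutropenia lasts longer than 7 days (despite holding umbralisib), interrupt acalabrutinib until Grade" a stated recovery level. A split on terminology therefore does not remove the conflict.

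**Is there a precedence rule?** The only tie-break in Section 7 is the last note under the dose-reduction table. It tells sites to apply the stricter recommendation when toxicities occur together. It does not address a general bullet that disagrees with a row.

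**Re-escalation.** The two texts compare as follows.

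- Condition: the general note needs a finding that the event was unrelated, plus Study PI consultation. The liver row needs only that the toxicity has not recurred after a full cycle. The row is marked for discussion with the Study PI, as are all Grade 3 or higher liver events, so the one missing element is the finding of unrelatedness. The liver section also says the toxicity could be due to either oral drug.
- Target: the umbralisib ladder is 800, 600, 400 mg. The first Grade 3 or higher liver event restarts umbralisib at 400 mg, and the 3rd-occurrence rule resumes it at 400 mg. One level up from 400 mg is 600 mg. The general exception returns to the previous dose, which for a patient moved directly from 800 to 400 mg would be 800 mg. The two texts can therefore differ in target as well as in condition.

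**The case against.** The best defense is that the specific row controls. Section 7.0 is titled as guidelines, Table 7.1.1 as recommended modifications, and the bullets refer the reader to the tables. The permissive bullet agrees with the rows. Several rows depend on the investigator's attribution, so some variation between sites is intended. All of that stands, and many sites would probably follow the row. But the protocol never says that the row overrides the bullet, and the bullet is written as a requirement. Intended discretion over attribution is also different from two instructions that disagree once attribution is settled.

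On re-escalation the defense is stronger. At the 2nd Grade 3 or higher liver event the row ordinarily discontinues umbralisib and resumes acalabrutinib. A 3rd event on that path arises off umbralisib, and the row then stops acalabrutinib and brings umbralisib back. This can fairly be read as re-attribution to acalabrutinib, close to what the general exception covers. What survives is a wording gap, not a flat contradiction.

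A reader might also try to size the problem by dividing the maximum delay by planned induction: 8 x 7 = 56 days over 6 x 28 = 168 days, or 33%. The documents do not support that as lost exposure. Section 5.2 fixes the cycle at 28 days only when there is no toxicity delay, and induction is defined as 6 cycles, so a hold may lengthen induction instead of removing doses. In the neutropenia row acalabrutinib is interrupted anyway once Grade 4 exceeds 7 days. While Grade 4 persists, the two readings therefore differ by about 7 days; a longer gap needs improvement below Grade 4 without reaching the recovery level.

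**Conclusion.** The interruption conflict holds. Three rows directly contradict the mandatory bullet, two more state no umbralisib hold where the bullet would require one, and nothing says which text governs. Two sites can each follow the protocol and treat the same event differently. The conclusion assumes only that a drug the table delays or holds counts as interrupted, and that the protocol text is what sites work from.

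The re-escalation point is secondary: the liver row carries Study PI discussion but no requirement that the event be found unrelated.

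The size of any consequence is unknown. A reader might infer that the affected rows are common or that the CR result is at risk. The documents show neither. They give no rate for umbralisib-attributed Grade 4 neutropenia, describe pneumonitis with umbralisib as minimal, and contain no figure linking hold practice to exposure or CR. The case for changing the text rests on safety and consistency, not on a measured bias.

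**What to change.** Reconcile the last interruption bullet in Section 7.1 with the Table 7.1.1 rows for neutropenia, thrombocytopenia, Grade 1-2 pneumonitis and Grade 2 or lower diarrhea, and state whether the bullet or the row governs when they differ. In the acalabrutinib-attributed rows, say explicitly what happens to umbralisib. Check the remaining rows against the bullet in the same pass. In the liver row, state whether the step up is an intended exception to the re-escalation note and, if so, on what condition and to which dose level. Which clinical rule applies in each case is for the sponsor's clinical team.

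The cost is a wording amendment and a memo to the sites. Sample size, endpoint definitions and analysis do not change.

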3.1 Inclusion Criteria

Informed Consent and Willingness to Participate

___1. Documented informed consent of the participant and/or legally authorized representative.

- Assent, when appropriate, will be obtained per institutional guidelines

Nature of Illness and Illness Related Criteria

___2. Histologically confirmed mantle cell lymphoma with documentation of monoclonal CD20+ B cells that have a chromosome translocation t(11;14)(q13;q32) and/or overexpress cyclin D1.

___3. Age \geq 65 years; or \geq 50 years and deemed ineligible for aggressive induction therapy or autologous stem cell transplant by the investigator, or unwilling to undergo aggressive induction; or \geq 18 years with documented del(17p), or TP53 mutation, or complex karyotype (CK) by cytogenetics and/or FISH studies.

___4. Requiring treatment for MCL, and for which no prior systemic anticancer therapies have been received (local radiotherapy not exceeding a total dose of 20 Gy at least 2 weeks prior the first dose of study therapy is allowed).

___5. Measurable disease by CT or PET/CT scan with one or more sites of disease \geq 1.5 cm in longest dimension (including splenomegaly), or bone marrow involvement with or without malignant lymphocytosis.

___6. ECOG \leq 2 ([Appendix A](#)).

Clinical Laboratory and Organ Function Criteria

___7. Without bone marrow involvement: ANC \geq 1000/mm ³ With bone marrow involvement: ANC \geq 500/mm ³ NOTE: Growth factor is not permitted within 7 days of ANC assessment unless cytopenia is secondary to disease involvement.	ANC:	Date:
___8. Without bone marrow involvement: Platelets \geq 75,000/mm ³ With bone marrow involvement: Platelets \geq 30,000/mm ³ NOTE: Platelet transfusions are not permitted within 7 days of platelet assessment unless cytopenia is secondary to disease involvement.	Plts:	Date:
___9. Total bilirubin \leq 1.5 X ULN or \leq 3X ULN for Gilbert's disease.	ULN: Bil:	Date:
___10. AST \leq 2.5 x ULN	ULN: AST:	Date:
___11. ALT \leq 2.5 x ULN	ULN: ALT:	Date:

Patient MRN (COH Only)	Patient Initials (F, M, L):
Institution:	

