	
• If toxicity is suspected to be related to acalabrutinib by the investigator (e. g. based on timing of toxicity occurrence during the cycle), delay acalabrutinib until Grade \leq 1 or baseline, thereafter, resume acalabrutinib at current dose level. For recurrences, acalabrutinib and/or umbralisib may be dose reduced. 
If applicable, delay ublituximab until Grade \leq 3 and, if present, neutropenic fever or infection is resolved; thereafter, resume ublituximab at full dose and schedule.

Thrombocytopenia	
Grade \leq 3 thrombocytopenia	
Provide supportive care as warranted.
 
Maintain current dose and schedule of acalabrutinib.
 
Maintain current dose of umbralisib.
 
If applicable, maintain full dose and schedule of ublituximab.

Grade 3 thrombocytopenia with bleeding, or Grade 4 thrombocytopenia	
Provide supportive care as warranted.
 
• If toxicity is suspected to be related to umbralisib by the investigator (e. g. based on timing of toxicity occurrence during the cycle):
1st occurrence:
- Delay acalabrutinib and umbralisib until Grade \leq 1 or baseline; thereafter, resume both acalabrutinib and umbralisib at current dose level.2nd occurrence:
- Same as for 1st occurrence, but resume umbralisib at next lower dose level (dose reduction).3rd occurrence:
- Same as for 1st occurrence, but resume both umbralisib and acalabrutinib at next lower dose level (dose reduction).4th occurrence:
- Discontinue both acalabrutinib and umbralisib. 
Delay ublituximab until Grade \leq 3; thereafter, resume ublituximab at full dose and schedule.

	
 • If toxicity is suspected to be related to acalabrutinib by the investigator (e. g. based on timing of toxicity occurrence during the cycle), delay acalabrutinib until Grade ≤ 1 or baseline, thereafter, resume acalabrutinib at current dose level. For recurrences, acalabrutinib and/or umbralisib may be dose reduced. 
Delay ublituximab until Grade ≤ 3; thereafter, resume ublituximab at full dose and schedule.

--	---

Pulmonary toxicity (pneumonitis) & Related Infections*	

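### Table 7.1.1, Grade 4 neutropenia or neutropenic fever/infection: when acalabrutinib is the suspected cause, its restart does not require fever or infection to have resolved; every other stated restart in the row does

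*Combined protocol and SAP*

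**What the plan says.** The row is triggered by Grade 4 neutropenia or by neutropenic fever or infection, so fever or infection can bring a patient into it without a Grade 4 count. It then divides by suspected cause.

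**Umbralisib suspected.** Acalabrutinib continues at the first and second occurrence unless the neutropenia persists: "If grade 4 neutropenia lasts longer than 7 days (despite holding umbralisib"). In that case the instruction is to "interrupt acalabrutinib until Grade \leq 1 or baseline and, if present, neutropenic fever or infection is resolved; thereafter, resume acalabrutinib at current dose level". At the third occurrence both oral drugs are held: "Delay umbralisib and acalabrutinib until Grade \leq 1 or baseline and, if present, neutropenic fever or infection is resolved".

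**Acalabrutinib suspected.** Acalabrutinib is held at once, and the instruction is to "delay acalabrutinib until Grade \leq 1 or baseline, thereafter, resume acalabrutinib at current dose level. For recurrences, acalabrutinib and/or umbralisib may be dose reduced". The ublituximab line directly below reads: "If applicable, delay ublituximab until Grade \leq 3 and, if present, neutropenic fever or infection is resolved; thereafter, resume ublituximab at full dose and schedule".

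Two other provisions bear on the reading. Section 7.1 defines baseline: "Baseline values are from the last values obtained prior to treatment". Section 3.1 sets a low neutrophil floor for some patients: "With bone marrow involvement: ANC \geq 500/mm" (per mm³).

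**The concern.** The gap is in the restart condition, not in what happens at onset. For the same drug and the same event, the restart rule is looser when acalabrutinib is the suspected cause than when it is not. Read literally, a site could restart acalabrutinib on the neutrophil count alone while the patient is still febrile or infected.

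Table 6.2.3 lists serious infections, including fatal ones, as an acalabrutinib risk, and Section 12.4.2 counts febrile neutropenia among the events that can halt accrual. With four participating sites working from one table, the row could also be applied differently from site to site. Nothing in the primary analysis depends on it.

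**Working it through.** The plan gives no figure for this point. The main check is a comparison of the text, followed by a rough estimate of how many patients could be involved.

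**Step 1. Restart instructions in the row**

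| Suspected cause | Occurrence | Drug restarted | Count condition | Fever/infection resolved? |
|---|---|---|---|---|
| Umbralisib | 1st | Umbralisib | Grade ≤1 or baseline | Required |
| Umbralisib | 1st, if Grade 4 exceeds 7 days | Acalabrutinib | Grade ≤1 or baseline | Required |
| Umbralisib | 2nd | As for 1st, umbralisib reduced | As for 1st | Required, by reference |
| Umbralisib | 3rd | Both oral drugs | Grade ≤1 or baseline | Required |
| Umbralisib | Any | Ublituximab | Grade ≤3 | Required |
| Acalabrutinib | Any | Acalabrutinib | Grade ≤1 or baseline | **Not stated** |
| Acalabrutinib | Any | Ublituximab | Grade ≤3 | Required |

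The fourth occurrence in the umbralisib branch is discontinuation, so no restart condition applies. Leaving aside the second occurrence, which works by reference, six instructions are written out and five carry the condition. The acalabrutinib branch gives no restart rule for umbralisib at all.

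**Step 2. Does the count condition already cover the fever?** In the umbralisib branch the row uses the same phrase, Grade ≤1 or baseline, and then adds the fever/infection condition separately. If the phrase covered fever, the addition would be redundant. The omission is therefore at best ambiguous.

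**Step 3. Can the count condition be met with fever unresolved?** Yes. Baseline is the last pre-treatment value, and a patient with marrow involvement may enrol with an ANC of 500/mm³. Such a patient, brought into the row by neutropenic fever, can be at baseline count while still febrile.

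**Step 4. Do other rules close the gap?** Only in part.
- For Grade ≥3 pulmonary toxicity and related infections the table says: "Hold acalabrutinib and ublituximab until complete resolution". The Grade 1–2 row keeps acalabrutinib going.
- The row for other non-hematological events holds acalabrutinib for Grade ≥3 events. Section 7.1 applies the stricter rule when toxicities coincide, so a separately recorded Grade ≥3 infection would be caught.
- Table 6.2.2 lists febrile neutropenia under blood and lymphatic disorders, so the non-hematological row does not clearly reach it.
- The general statement in Section 7.1 that all drugs are held during an interruption adds no fever condition for restarting.

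**Step 5. Size.** The closest documented rate is serious febrile neutropenia on acalabrutinib monotherapy in Table 6.2.2.
- Rate: 16/1079 = 0.01483, or 1.48% (Clopper–Pearson 95% CI 0.85% to 2.40%).
- Expected cases: 24 × 0.01483 = 0.36; 27 × 0.01483 = 0.40.
- Range across the CI: 24 × 0.00850 = 0.20 to 27 × 0.02397 = 0.65.
- Chance of at least one: 1 − (1 − 0.01483)^24 = 0.301; 1 − (1 − 0.01483)^27 = 0.332.

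The rate for the three-drug combination is not in the documents. Under assumed rates for 24 and 27 patients:
- 3%: 0.72 to 0.81 cases
- 5%: 1.20 to 1.35 cases
- 10%: 2.4 to 2.7 cases

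**The case against.** The missing clause itself is not in dispute. The case on the other side concerns how much it matters.

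- **Natural reading.** The branch deals with a toxicity that includes neutropenic fever or infection, and Section 7.1 frames interruptions as lasting until the toxicity resolves. Baseline for a fever is no fever. If baseline meant the count alone, a patient whose ANC never fell below baseline would have a delay that ended as it began. This is a fair reading and probably what many investigators would do. It does not remove the ambiguity, because the same row states the two conditions separately everywhere else.
- **Existing safeguards.** Infections, including neutropenic sepsis, are listed under infections in Table 6.2.2, so a Grade ≥3 infection falls under stricter rows. This stands. What remains is mainly neutropenic fever without a Grade ≥3 infection, attributed to acalabrutinib and outlasting the count criterion, chiefly through the baseline alternative.
- **Fever is not always a bar to acalabrutinib.** In the umbralisib branch acalabrutinib can continue through neutropenic fever at the first two occurrences. This weakens any claim that exposure during fever is regarded as unsafe in itself. There, however, acalabrutinib is not the suspected drug, and once it is held in that branch, restarting it requires resolution.
- **Guidance only.** The table gives recommendations, and infections are managed by institutional practice. Nothing compels a restart in a febrile patient. That limits the harm but is no reason to leave the table inconsistent on a safety restart.
- **The rate does not measure the gap.** It covers serious events on monotherapy over a median exposure of 28.5 months. This stands: 30% to 33% is the chance of any such event at that rate, not of a patient meeting the gap, for which the documents give no figure.

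**Conclusion.** The concern holds. The acalabrutinib restart in the acalabrutinib-suspected branch is the only one of six written restart instructions in the row without the fever/infection condition, and no other provision supplies it in full. The same sentence appears in the thrombocytopenia row, where no fever clause is needed, so carried-over wording is a plausible explanation, though that is inference.

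The practical effect is small: well under one expected case of serious febrile neutropenia at the monotherapy rate, and one to three at assumed combination rates of 5% to 10%. Only a subset of cases would meet the gap. These figures assume that the monotherapy rate, or the assumed rates, carry over to this regimen and population. This is a low-frequency safety inconsistency worth correcting; it has no bearing on sample size, alpha or power.

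**What to change.** In the acalabrutinib-suspected branch of this row, make resumption of acalabrutinib depend on both conditions: count recovery to Grade ≤1 or baseline, and resolution of any neutropenic fever or infection. The wording already exists for the same drug in the other branch, "interrupt acalabrutinib until Grade \leq 1 or baseline and, if present, neutropenic fever or infection is resolved; thereafter, resume acalabrutinib at current dose level", and can be reused with the opening verb changed to delay. The sentence on recurrences can stay as it is.

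The cost is one clause in the next amendment and a slightly longer acalabrutinib hold in a few patients, subject to the existing 8-week maximum delay in Section 7.1.
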